8.2 Sample size determination

With respect to the primary study endpoint of the time interval from administration of misoprostol to active phase of labor (greater than or equal to 6 cm dilation), shorter times are considered better. Based on a previous published data, the mean time interval from vaginal misoprostol administration to active phase of labor was 12.0 hours (standard deviation (SD)=5.9 hours) [9] and the mean time interval from oral misoprostol administration to active phase of labor was 9.9 hours (SD=7.1 hours). [10] Using these standard deviations and a non-inferiority margin of 4 hours, a sample size of 92 patients (46 per group) would provide 80% power to

detect non-inferiority of oral misoprostol compared to vaginal misoprostol with respect to the time interval from administration of misoprostol to active phase of labor using a one-sided Mann-Whitney test having a significance level of 0.025. Factoring in a 15% drop-out rate, our target sample size is 110 subjects.

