8.3 Statistical methods

Analyses will invoke an intent-to-treat paradigm, wherein all randomized subjects are included according to their randomized treatment arm, regardless of actual treatment received. Data will be summarized using descriptive statistics for continuous variables (mean, standard deviation, number of observations, and percentiles) and frequency statistics (frequencies and percentages) for categorical variables. Univariate and bivariate distributions will be inspected in order to address any missing data, inconsistent responses, outliers, and data entry errors.

The primary study endpoint will be the time interval from administration of misoprostol to active phase of labor (greater than or equal to 6 cm dilation) and shorter time is considered better. The difference between the treatment arms (oral misoprostol – vaginal misoprostol) will be denoted by Δ and the non-inferiority margin will be set to $\delta=4$ hours. Thus to test for non-inferiority of oral misoprostol compared to vaginal misoprostol the null hypothesis is $H_0: \Delta \geq 4$ hours and the alternative hypothesis is $H_a: \Delta < 4$ hours. The distribution of the time interval from administration of misoprostol to active phase of labor (greater than or equal to 6 cm dilation) is expected to be skewed. Therefore, to test for non-inferiority of oral misoprostol compared to vaginal misoprostol with respect to the primary endpoint, a one-sided Mann-Whitney test will be used where the non-inferiority margin will be set to 4 hours. The upper bound of the one-sided 97.5% confidence interval for testing non-inferiority will be constructed using the Mann-Whitney test as described by Rothman et al. [11] If the upper bound of the one-sided 97.5% confidence interval is less than the non-inferiority margin of 4 hours, then the null hypothesis will be rejected. In the event the primary endpoint is normally distributed, a one-sided, two-sample t-test will be utilized to test for non-inferiority with corresponding one-sided 97.5% confidence interval.

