As detailed in Section 1.3, there are numerous secondary endpoints for this study. Secondary continuous outcomes (e.g., time interval from administration of misoprostol to initiation of oxytocin for continued augmentation of labor and time interval from administration of misoprostol to vaginal delivery) will be compared between the two treatment groups using a two-sample t-test or Mann-Whitney test, as appropriate, based on the distribution of the outcome. Additionally, as a secondary analysis, Kaplan-Meier survival curves will be constructed for these two time to event outcomes. Secondary categorical outcomes (e.g., Section 1.3 secondary endpoints 3-15 which includes Cesarean section rate and rate of tachysystole) will be compared between the two groups using a chi-square test (or Fisher's exact test if the expected cell counts are small).

While every attempt will be made to collect complete data and prevent participant drop-out, there is the possibility of drop-outs and other missed information. We expect the underlying mechanism of any missing data for this particular study to arise due to data that are missing-at-random (MAR). One reason the MAR assumption is expected for this study is because the two treatment arms are providing the same drug (misoprostol) but via different routes (oral vs. vaginal). The statistical methods and analyses that are planned for the primary and secondary outcomes are appropriate, and provide valid inference, under the MAR assumption. Although not expected for this study, if it appears the MAR assumption is not reasonable then we will use multiple imputation to handle the issue of missing data for analyses.

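### Section 8.3 claims too much for unadjusted tests under MAR and keeps multiple imputation for when MAR fails, with no departure model named; the likely effect is small

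*Combined protocol and SAP*

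**What the plan says.** All of the missing-data text except chart retrieval is in section 8.3.

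- **Tests.** For the primary endpoint, "The upper bound of the one-sided 97.5% confidence interval for testing non-inferiority will be constructed using the Mann-Whitney test"; if the times look normal, "a one-sided, two-sample t-test will be utilized to test for non-inferiority". Secondary continuous outcomes get a t-test or Mann-Whitney test. Secondary categorical outcomes "will be compared between the two groups using a chi-square test", or Fisher's exact test when expected counts are small. No covariate or stratum enters any of them, although section 7.4.3 stratifies randomization by parity.
- **Validity claim.** "The statistical methods and analyses that are planned for the primary and secondary outcomes are appropriate, and provide valid inference, under the MAR assumption".
- **Reason for expecting MAR.** One reason is given: "the two treatment arms are providing the same drug (misoprostol) but via different routes".
- **Fallback.** "if it appears the MAR assumption is not reasonable then we will use multiple imputation to handle the issue of missing data". No imputation model, variables, departure from MAR or criterion for judging MAR is stated.
- **Data review.** "Univariate and bivariate distributions will be inspected in order to address any missing data".

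Section 3.3.2 adds that chart data from withdrawn women may still be used. Section 8.2 allows for 15% drop-out.

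**The concern.** MAR lets missingness depend on anything observed, including parity. A two-sample test on the observed values conditions on arm only. It is sound if times are missing completely at random, if loss depends on arm alone, or in special cases such as the same parity-related loss in both arms with a constant shift. It is not sound if the link between parity and loss differs by arm. Stratified randomization balances parity at entry, not among the women whose times are observed.

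The fallback sits in the wrong place. Standard imputation works under MAR, where the plan does not use it. The plan calls on it when MAR fails, where it needs a stated departure model to help. Observed data cannot verify MAR, so looking at distributions can inform the trigger but cannot test it. That the arms share a drug says nothing about why a time would be missing.

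The trial's conclusion rests on one upper bound against 4 h. As written, no analysis would show how far missing times could move that bound.

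**Working it through.** **1. The plan's own figure.** Section 8.2 gives SDs of 5.9 and 7.1 h, a 4 h margin, one-sided alpha 0.025 and 80% power. Pooled SD = √((5.9² + 7.1²)/2) = 6.53 h. With a true difference of 0, a t-based calculation needs 43 per group; 43 × π/3 = 45.03, rounded up to 46, so 92 in total. 92/0.85 = 108.2, or 109 rounded up, close to the stated 110. The sample size is not in dispute.

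**2. Hand calculation under MAR.** Assumed, not in the documents: 55% nulliparous; nulliparous women 3 to 7 h slower; nulliparous loss 30% oral and 10% vaginal; multiparous loss 5% in both arms.
- Observed nulliparous share, oral: 0.55 × 0.70 / (0.55 × 0.70 + 0.45 × 0.95) = 0.385/0.8125 = 47.4%.
- Vaginal: 0.55 × 0.90 / (0.55 × 0.90 + 0.45 × 0.95) = 0.495/0.9225 = 53.7%.
- Gap 6.3 points. Bias in the mean difference = 0.063 × 3 to 7 h = 0.19 to 0.44 h, in favour of oral.
- Overall loss = (18.75% + 7.75%)/2 = 13.25%, within the plan's 15% allowance. The split by arm and parity is the assumption that matters.
- At one fifth of these rates the shares are 53.7% and 54.7%, and the bias is 0.03 to 0.07 h.
- For a categorical endpoint with an assumed 10 to 20 point parity difference, 6.3 points of imbalance give 0.6 to 1.3 percentage points.

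**3. Simulation.** 110 women, permuted blocks within parity, vaginal mean 12 h (section 8.2: "the mean time interval from vaginal misoprostol administration to active phase of labor was 12.0 hours"), total SD 6.5 h, skewed residuals, true difference 4.0 h; 16,000 runs per scenario.

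| Assumed loss | Estimate (h) | False non-inferiority, Mann-Whitney |
|---|---|---|
| None | 4.0 | 0.8–2.2% |
| As in step 2 | 3.5–3.8 | 2.8–3.4% |
| Step 2, arms swapped | 4.2–4.5 | 0.3–1.6% |
| Equal 20% nulliparous loss | 4.0 | 1.0–2.3% |
| One fifth of step 2 | 3.9–4.0 | 1.0–2.4% |

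The t-test gave 3.0–3.3% in the second row. Separate simulations of that row gave 2.6–3.2% for Mann-Whitney, and a smaller set of 3,200 runs gave 2.3–2.8%. Imputing on arm and parity returned the estimate to 4.0 h.

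A more opposed pattern (oral loss 25% nulliparous and 5% multiparous, vaginal the reverse; half nulliparous; parity gaps 2 to 6 h) gave 3.4–5.4%. A parity-stratified rank test on the same data gave 2.0%. In further simulations the stratified test stayed at 2.2–2.7%.

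**4. Imputation when MAR fails.** Assumed: oral times over 18 h missing 30% of the time, others 3%. The observed estimate was 3.3–3.4 h and imputation under MAR gave 3.4–3.5 h, leaving 75–97% of the bias. A second set of assumptions (12–18% missing, slower oral labours lost more often) gave biases of 0.41, 0.88 and 1.34 h before imputation and 0.37, 0.80 and 1.24 h after it, so about nine tenths remained. The same selective loss of slow times in the vaginal arm gave 4.4 h observed and 4.3–4.4 h imputed, which is conservative.

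**5. A plausible scale.** If 2 of 55 oral times are missing and truly 8 h longer than imputed, the mean difference moves by 2 × 8/55 = 0.29 h, or 0.29/4 = 7% of the margin.

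**The case against.** The strongest reply is that there may be almost nothing to impute. Withdrawn women's charts can be used (3.3.2), examinations are every 4 hours during misoprostol and every 2 hours afterwards (7.2), and participation ends at delivery (7.3). Harm also needs parity-related loss that differs by arm, and nothing in the documents points to that pattern. The reverse pattern is conservative. All of this stands and sets the priority. The 15% allowance does show that the plan expects some loss.

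A second reply is that imputation need not assume MAR and the wording leaves room for a departure model. That also stands. A reader might infer that the fallback is simply a wrong rule; the text supports only that it is misplaced and under-specified.

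A third is that imputation is not the only remedy. A parity-stratified rank test uses the existing stratum and held its level well. It belongs in the fix as an equal option.

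Two limits apply to the figures. The simulations used one common SD, while section 8.2 gives two. The 0.29 h in step 5 is a mean difference, which fits the t-test; the Mann-Whitney shift would move by about 0.24 h. The Kaplan-Meier curves in 8.3 cover two secondary times, not the primary endpoint.

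**Conclusion.** The concern holds in a limited form. The validity sentence is too broad for unadjusted tests, and the imputation fallback is misplaced and lacks a departure model. The first part follows from the text and needs no simulation.

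The size rests on assumed loss rates, nulliparous share and parity gap. Under the step 2 pattern the bias is about 0.2 to 0.5 h and false non-inferiority is about 3% against 2.5%. At low loss it is negligible.

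Three stronger readings are not supported:
- That these tests are always invalid under MAR. They hold in the cases listed above.
- That the plan tilts the trial towards non-inferiority. The direction depends on which arm loses which women, and the documents do not say.
- That this point covers women delivered by cesarean before 6 cm. Their primary time does not exist rather than being unrecorded, which is a separate matter.

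**What to change.** Rewrite the missing-data paragraph in section 8.3:

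1. Limit the validity statement to data missing completely at random, by arm only, or with equal parity-related loss in both arms and a constant shift.
2. Retrieve times from the chart first, and report the number missing by arm and parity.
3. For times still truly missing, name one method that conditions on parity, chosen before data review: either a parity-stratified rank test with its shift confidence bound, or multiple imputation under MAR using arm, parity and, if recorded, baseline Bishop score (an eligibility item in section 3.1). If imputation is chosen, state a pooling method that matches the primary test used.
4. Replace the trigger with a pre-specified tipping-point analysis. Add a delta to the imputed oral-arm times, the direction against non-inferiority, and report the delta at which the upper bound crosses 4 h. This step needs imputed values even if the rank test is chosen in item 3.
5. For secondary tests, report the number missing and state the narrower assumption.

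The cost is one paragraph, modest programming and possibly a slightly wider bound. In simulation with a true difference of 0 and a 5 h parity gap, imputation raised the mean upper bound by 0.04 h at 3.7% oral loss. A 4 h delta added 0.15 h at that loss and 0.78 h at 18.8% oral loss.

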9.0 Confidentiality, Privacy and Data Management

See the Research Data Plan Review Form

10.0 Data and Safety Monitoring Plan

10.1 Periodic evaluation of data

This study involves minimal risk to subjects as it involves standard methods for cervical ripening and induction of labor as stated by multiple collaborations including American College of Obstetricians and Gynecologists, Cochrane Review, and World Health Organization. Oversight for the conduct of the study will be provided by the PI, co-PI, and her mentoring team. They will ensure that all eligibility criteria and consent requirements are met prior to a subject's participation in study and that all study procedures and adverse event reporting occur according to the IRB approved protocol.

10.2 Data that are reviewed

Data collection for safety monitoring: Treatment emergent serious adverse events (TESAEs) are defined as uterine rupture, maternal death during her hospitalization, neonatal death (0-28 days of life) related to the study drug, and cesarean hysterectomy, and will be reported to the IRB within 24 hours of occurrence. Other adverse events that will be reviewed include postpartum hemorrhage requiring blood transfusion, surgical ICU admission, and neonatal NICU admission during mother's hospital admission.

10.3 Method of collection of safety information

All TESAEs (uterine rupture, maternal death during her hospitalization, neonatal death (0-28 days of life) related to the study drug, and cesarean hysterectomy) will be documented on study specific case report forms. Co-PI, with [name] as second contact, will be notified immediately to begin process of notifying the IRB within 24 hours if the event is a TESAE.

10.4 Frequency of data collection

Data will be collected as the patient is on Labor and Delivery during the time of study. Collected data should be entered into the REDCap system within one month's time of the subject participating in the study.

10.5 Individuals reviewing the data

The PI, [name] and Co-Investigator will review cumulative adverse events, early termination of study participation, and accrual every six months and report any issues requiring modification of the study or alteration of the risk:benefit ratio to the IRB immediately. The PI's will be assisted in reviewing the data by [name] and [name] with the Department of Public Health Sciences in the Division of Biostatistics and Bioinformatics.

10.6 Frequency of review of cumulative data

The data between the two study groups will be compared on six month intervals.

10.7 Statistical tests

At six month intervals, the percentage of participants experiencing adverse events will be compared between the two groups using Fisher's exact tests; however, stopping of the study will not be based on statistical significance. The statistical tests will be used as an aid to help inform the PIs of the safety of the study.

10.8 Suspension of research

If the total number of subjects experiencing one or more TESAE (defined as uterine rupture, maternal death during her hospitalization, neonatal death (0-28 days of life) related to the study drug, and cesarean hysterectomy) reaches 5, the trial will be stopped. This reflects a 2.3% prevalence rate (110 subjects with 110 singleton neonates are included in the trial for a prevalence of 5/220 subjects). Or if any two cases of uterine rupture, two cases of maternal death during her hospitalization, or two cases of neonatal death (0-28 days of life) related to the study drug, the trial will be stopped.

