1.3 Secondary Study Endpoints

1. Time interval from administration of misoprostol to initiation of oxytocin for continued augmentation of labor
2. Time interval from administration of misoprostol to vaginal delivery
3. Cesarean section rate
4. Rate of vaginal delivery within 24 hours
5. Rate of abandoning misoprostol for cervical ripening and switching to mechanical dilation for cervical ripening (ie, Foley balloon)
6. Rate of development of preeclampsia requiring magnesium sulfate administration
7. Rate of tachysystole
8. Rate of tachysystole causing non-reassuring fetal heart tones
9. Rate of need for tocolysis
10. Rate of chorioamnionitis
11. Rate of meconium stained fluid
12. Neonatal morbidity (composite outcome)
 - a. Apgar of less than 7 at 5 minutes
 - b. Fetal arterial umbilical cord gas with pH of less than 7 or base deficit great than 12
 - c. NICU admission within 4 hours of delivery
13. Maternal side effects
 - a. Rate of anti-emetic use
 - b. Rate of diarrhea
14. Treatment emergent serious adverse events
 - a. Uterine rupture
 - b. Cesarean hysterectomy
 - c. Maternal death during her hospitalization
 - d. Neonatal death (0-28 days of life) related to the study drug
15. Adverse events
 - a. Postpartum hemorrhage requiring blood transfusion
 - b. Maternal surgical ICU admission
 - c. Neonatal NICU admission during mother's hospital admission

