3.3 Early Withdrawal of Subjects

3.3.1 Criteria for removal from study

Individual subjects who desire to be withdrawn from the study or who withdraw their consent to be in the study at any time will be removed from the study and continue their care in a routine fashion. If the patient experiences an unexpected allergic reaction to the study drug (evidenced by hives, rash, swelling, or difficulty breathing), the patient will be immediately withdrawn from study participation and will no longer receive the study drug. If the patient experiences a serious adverse event (uterine rupture) while taking study drug, she will be removed from the study and no longer receive study drug. Any serious adverse event that occurs after delivery (maternal death during hospitalization, neonatal death during hospitalization, cesarean hysterectomy) does not warrant removal from study since study drug would already be terminated.

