19.6 Stopping Rules

If the total number of subjects experiencing one or more serious adverse events (defined as uterine rupture, maternal death during her hospitalization, neonatal death during maternal hospitalization, and cesarean hysterectomy) reaches 5, the trial will be stopped. This reflects a 2.3% prevalence rate (110 subjects with 110 singleton neonates are included in the trial for a prevalence of 5/220 subjects). Or if any two cases of uterine rupture, two cases of maternal death during her hospitalization, or two cases of neonatal death (0-28 days of life) related to the study drug, the trial will be stopped.

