20.1.2 Safety Monitoring

On the listed protocol that investigators will follow while carrying out the study, will be the list of treatment emergent serious adverse events (TESAEs). Treatment emergent serious adverse events are defined as maternal death during hospital admission, neonatal death (0-28 days of life) related to the study drug, uterine rupture, or cesarean hysterectomy. If a TESAE happens the Co-investigator will be immediately paged and notified. If no response within 4 hours, the Principal Investigator, [name], will be paged.

The Principal Investigator will confirm that the TESAE are correctly entered into the adverse event (AE) case report forms by the Co-investigator; be available to answer any questions that the Co-investigator may have concerning AEs; and will notify the IRB and FDA all TESAEs. All assessments of AEs will be made by a licensed medical professional who is an investigator on the research.

The Co-investigator will complete the appropriate report form and logs; assist the PI to prepare reports and notify the IRB and FDA of all Unanticipated Problems/TESAE's.

The Clinical Trial Monitoring Team will confirm that the TESAEs and AEs are correctly entered into the case report forms. The monitoring team will also confirm that the adverse events are consistent with the source documents and are reported to the appropriate regulatory bodies as required.

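### The TESAE lists and the five-subject stopping count name only cesarean hysterectomy, so a hysterectomy after vaginal delivery is not counted

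*Combined protocol and SAP*

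**What the plan says.** The TESAE list appears in several sections of the combined protocol and SAP, and its hysterectomy item is always worded the same way.

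- Section 1.3, item 14b: "Cesarean hysterectomy".
- Section 10.2 ties the list to a deadline: "and cesarean hysterectomy, and will be reported to the IRB within 24 hours of occurrence". Section 10.3 repeats the list and the deadline.
- Section 10.8, the five-subject limit: "neonatal death (0-28 days of life) related to the study drug, and cesarean hysterectomy) reaches 5, the trial will be stopped".
- Section 19.6 restates the limit with its own list: "neonatal death during maternal hospitalization, and cesarean hysterectomy) reaches 5, the trial will be stopped".
- Section 20.1.2, which governs paging and notice to the IRB and FDA, ends its list with "neonatal death (0-28 days of life) related to the study drug, uterine rupture, or cesarean hysterectomy".

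Section 3.3.1 uses the same term in an example: "Any serious adverse event that occurs after delivery (maternal death during hospitalization, neonatal death during hospitalization, cesarean hysterectomy) does not warrant removal from study".

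Sections 10.8 and 19.6 add a second trigger, which names no hysterectomy: "Or if any two cases of uterine rupture, two cases of maternal death during her hospitalization, or two cases of neonatal death" (the last of these limited to deaths related to study drug). Section 10.8 explains the limit of five by a proportion: "110 subjects with 110 singleton neonates are included in the trial for a prevalence of 5/220 subjects".

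No section defines cesarean hysterectomy more broadly. None lists hysterectomy after vaginal birth, or hysterectomy from any cause.

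**The concern.** Taken at its word, the term covers a hysterectomy done with a cesarean. The trial induces labor and follows time to vaginal delivery and vaginal delivery within 24 hours as endpoints, so many of its subjects should deliver vaginally. Emergency loss of the uterus after a vaginal birth is the same harm to the woman as loss at cesarean. Yet only the latter is a TESAE, counts toward the limit and carries the 24-hour report. Rupture, maternal death and neonatal death are all counted whatever the mode of delivery; hysterectomy is the only listed item that is not.

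The count matters because it is one of only two fixed stopping triggers. Section 10.1 places oversight with the investigators and their mentoring team, and section 10.7 says that statistical significance will not stop the study. The six-monthly review otherwise rests on judgment.

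**Working it through.** **The plan's own figure.** Five events over 110 women plus 110 neonates is 5 / 220 = 0.0227, or 2.3%. The stated figure reproduces. It describes the threshold and does not depend on which kinds of hysterectomy are listed.

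**Is the list closed?** Section 10.8 counts TESAEs and section 19.6 counts serious adverse events. Each then defines its term in parentheses by naming the events, and neither refers to the general definition of a serious adverse event in 19.1. Both lists are therefore closed. (They differ on neonatal death. That is a separate matter and does not affect this point.)

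**Applying the lists to four records.**

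| Record | Listed item met | Added to the count as written | Added if any peripartum hysterectomy counts |
|---|---|---|---|
| Cesarean, then hysterectomy | Cesarean hysterectomy | 1 | 1 |
| Vaginal delivery, uterine rupture, hysterectomy | Uterine rupture | 1 | 1 |
| Vaginal delivery, transfused hemorrhage, hysterectomy; no rupture or death | Item 15a only (other adverse event) | 0 | 1 |
| Vaginal delivery, hysterectomy; no rupture, death, transfusion or surgical ICU stay | None of the named maternal safety events | 0 | 1 |

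The gap is confined to the last two rows. Where rupture or maternal death also occurs, the subject is counted through that item.

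**Effect on the limit.** Suppose four subjects have a listed TESAE and a fifth has a hysterectomy after vaginal delivery.

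- As written: 4 + 0 = 4, below 5, and the trial continues.
- With the item widened: 4 + 1 = 5, and the trial stops.

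The example can arise without the two-case trigger having fired. One rupture, one maternal death and two cesarean hysterectomies, in four different women, make 1 + 1 + 2 = 4 with no named pair.

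**Expected number missed.** The documents give no hysterectomy rate and no split by mode of delivery. If the rate of hysterectomy after vaginal delivery, without another listed event, were 0.1% or 0.5% of all subjects (both assumed), the expected number among 110 women would be 110 × 0.001 = 0.11 or 110 × 0.005 = 0.55. Both are below one.

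**The case against.** The event would not go unseen. An emergency hysterectomy fits the general definition of a serious adverse event in 19.1. Section 19.3 requires prompt review of its cause and seriousness. Sections 19.2 and 19.4 send it to the IRB if it is judged unexpected and probably related, and 20.1.2 covers unanticipated problems. Transfusion or surgical ICU admission would be reviewed under 10.2, and 10.5 brings cumulative adverse events to a six-monthly review, with immediate report of any change in risk and benefit. All of this stands. What it does not do is add to the count or, since the event is not a TESAE, start the 24-hour report.

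Three stronger readings are tempting, and the documents support none of them.

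- A reader might infer that the stopping rule is less sensitive than the protocol claims. The protocol claims no sensitivity; it only equates five events with 5/220. Any probability of stopping would need assumed event rates and would have to include the two-case trigger.
- A reader might infer that the comparison of arms is biased, because mode of delivery is itself an outcome (endpoint 3). The dependence exists in principle. With about 110 / 2 = 55 women per arm, and fewer than one such event expected in the whole trial at the assumed rates, it remains theoretical. The six-monthly tests in 10.7 also cover adverse events generally and do not decide stopping.
- A reader might take 3.3.1, which places the event after delivery, as proof that the authors meant any route. A hysterectomy at cesarean also follows delivery of the infant, so this is weak evidence of intent and not an internal contradiction.

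**Conclusion.** The gap is real on the text, and no other section closes it. A hysterectomy after vaginal delivery, without rupture or maternal death, adds 0 to the five-subject count and triggers no 24-hour TESAE report. Because a stated rule miscounts the event, this is more than a missing detail.

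Its practical size is small. That judgment rests on the assumption that such events are rare, since the documents give no rate. The change would make the count and the report of a catastrophic maternal event correct; it is unlikely to alter the course of the trial. No probability of stopping and no bias between arms should be attached to it. Low priority, and worth doing because it costs almost nothing.

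**What to change.** In section 1.3 item 14b and sections 3.3.1, 10.2, 10.3, 10.8, 19.6 and 20.1.2, replace cesarean hysterectomy with *peripartum hysterectomy (at cesarean or after vaginal delivery, during the delivery hospitalization)*. Count it in the TESAE total, the 24-hour report and endpoint 14b whatever the mode of delivery. Leave the limit of five, the two-case trigger and the stated 2.3% as they are.

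The cost is a wording amendment in seven places and one line on the TESAE case report form. It needs no added visit or procedure, because a hysterectomy is in the hospital chart in any case. The one small downside is that the limit of five could be reached slightly sooner.
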